7.1.2 Definition of Serious Adverse Event

An SAE is an AE occurring during any study phase (i.e., screening, run-in, treatment, and wash-out, follow-up), at any dose of the study drugs that fulfills one or more of the following criteria:

- Results in death
- Is immediately life-threatening
- Requires in-patient hospitalization or prolongation of existing hospitalization
- Results in persistent or significant disability or incapacity
- Is a congenital abnormality or birth defect in the offspring of the patient
- It is considered a significant medical event by the investigator based on medical judgment (e.g., may jeopardize the patient or may require medical/surgical intervention to prevent one of the outcomes listed above).

7.2 Adverse Event Reporting Period

All AEs, SAEs, and other reportable safety events that occur after the ICF is signed but before study treatment initiation must be reported by the investigator if the event causes the patient to be excluded from the study, or is the result of a protocol-specified intervention, including but not limited to washout or discontinuation of usual therapy, diet, or a procedure.

- The investigator must report all AEs from the time of first protocol-specific intervention through 30 days following cessation of study treatment.
- All AEs meeting serious criteria from the time of first protocol-specific intervention through 30 days following cessation of study treatment or before the initiation of a new anticancer therapy, whichever comes first, must be reported by the investigator.
- Additionally, any SAE brought to the attention of an investigator at any time outside of the period specified above must be reported immediately by the investigator if the event is considered related to the study treatment. These events must be followed until they are resolved or stabilized

Information to be reported in the description of each AE includes:

- AE (verbatim)
- Severity grade (CTCAE Grade 1–5)
- The date of onset and resolution of the AE
- Whether the AE is serious or not, where an SAE is defined as in Section **7.1.2**.
- Investigator causality assessment with respect to the study treatment (yes or no)
- Action taken with respect to the study treatment (none, temporarily interrupted, dose reduced, permanently discontinued, unknown, not applicable)

Proprietary Information of MD Anderson

Protocol 2020-1241

19 October 2022

- Outcome (not recovered/not resolved, recovered/resolved, recovering/resolving, recovered/resolved with sequelae, fatal, unknown)

7.3 Assessment of Adverse Events

All AEs and SAEs, whether reported by the patient, discovered by study personnel during questioning, or detected through a physical exam, laboratory test, or other means will be reported appropriately. Each reported AE or SAE will be described by its duration (i.e., start and end dates), regulatory seriousness criteria if applicable, suspected relationship to the study treatment (see following guidance), and actions taken.

AE Attribution:

The investigator (or physician designee) is responsible for verifying and providing source documentation for all AEs and assigning the attribution for all AEs for patients enrolled.

Attribution: The determination of whether an AE is related to a medical treatment or procedure.

To ensure consistency of AE and SAE causality assessments, investigators should apply the following general guideline:

Definite - the AE is clearly related to the investigational agent.

Probable - the AE is likely related to the investigational agent.

Possible - the AE may be related to the investigational agent.

Unlikely - The AE is doubtfully related to the investigational agent.

Unrelated - The AE is clearly NOT related to the investigational agent.

Expected AEs are those AEs that are listed or characterized in the current United States Product Insert.

Unexpected AEs are those not listed in the current IB or not identified. This includes AEs for which the specificity or severity is not consistent with the description in the IB.

7.4 Procedures for Eliciting, Recording, and Reporting Adverse Events

7.4.1 Eliciting Adverse Event Information

A consistent methodology of non-directive questioning should be adopted for eliciting AE information at all patient evaluation time points.

7.4.2 Specific Instructions for Recording Adverse Events

AEs and SAEs will be recorded in the Molecular and Clinical Data Integrated Platform (MOCLIP).

Proprietary Information of MD Anderson

Protocol 2020-1241

19 October 2022

Investigators should use correct medical terminology/concepts when reporting AEs or SAEs. Colloquialisms and abbreviations should be avoided.

This study will follow the NCI Recommended AE Recording Guidelines for Phase II studies, as per the below **Table 17**.

Table 17: Recommended Adverse Event Recording Guidelines

Attribution	Grade 1	Grade 2	Grade 3	Grade 4	Grade 5
Unrelated	Phase I	Phase I	Phase I Phase II	Phase I Phase II Phase III	Phase I Phase II Phase III
Unlikely	Phase I	Phase I	Phase I Phase II	Phase I Phase II Phase III	Phase I Phase II Phase III
Possible	Phase I Phase II	Phase I Phase II Phase III			
Probable	Phase I Phase II	Phase I Phase II Phase III			
Definitive	Phase I Phase II	Phase I Phase II Phase III			

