3 STUDY ENDPOINTS

3.1 Efficacy endpoints:

Radiographic tumor assessments (CT scan or MRI) will be performed by RECIST 1.1. The endpoints of efficacy assessment include:

- ORR described as the proportion of patients who achieve CR or PR by the combination therapy.
- PFS described as the time from study treatment initiation to the date of disease progression or death due to any cause. Patients without progression will be censored at the time of the last follow up.
- OS described as the time from study treatment initiation to the date of death due to any cause. Patients without progression will be censored at the time of the last follow up.

3.2 Safety endpoints:

- Incidence of AEs including but not limited to treatment-emergent AEs, serious AEs, deaths, and clinical laboratory abnormalities, as assessed by the NCI CTCAE v5.0.
- DLT is defined as any of the following adverse reaction observed during first cycle of treatment, and assessed as *possibly*, *probably* or *definitely* related to treatment with copanlisib in combination with fulvestrant. NCI CTCAE v. 5.0 will be used for grading of AEs.

- **Non-hematological AEs:**

- Grade ≥ 2 non-infectious pneumonitis
- Laboratory abnormalities meeting Hy's law criteria (AST or ALT $>3 \times$ ULN with concomitant TB $>2 \times$ ULN). (FDA 2009)
- Any \geq Grade 3 AE, except:
 - Grade 3 fatigue lasting ≤ 5 days
 - Grade 3 nausea or vomiting that has resolved to grade ≤ 2 within 3 days after standard antiemetic therapies
 - Grade 3 diarrhea that has resolved to grade ≤ 2 within 3 days after standard antidiarrheal therapies
 - Isolated laboratory findings not associated with signs or symptoms and lasting less than 3 days, including but not limited to grade 3/4 alkaline phosphatase, uric acid, amylase, and lipase elevations, and grade 3 electrolyte laboratory abnormalities hypophosphatemia, hypokalemia,

Proprietary Information of MD Anderson

Protocol 2020-1241

19 October 2022

hypocalcemia, or hypomagnesemia responsive to supplementation and grade 3/4 lymphopenia.

- Grade 3 hyperglycemia lasting ≤ 7 days

- **Hematological AEs:**

- Grade 4 neutropenia lasting ≥ 7 consecutive days
- Grade 3 and grade 4 febrile neutropenia
- Grade 4 anemia (in the absence of disease progression in bone marrow)
- Grade 3 anemia requiring blood transfusion
- Grade 4 thrombocytopenia of any duration
- Grade 3 thrombocytopenia lasting ≥ 7 consecutive days or associated with bleeding

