4.1.3 Safety Follow-Up

The safety follow-up visit should be conducted 30 (+ 5) days after the last dose of study treatment or before the initiation of a new anticancer therapy, whichever comes first. AEs that occur prior to the safety follow-up visit will be recorded as per the NCI Adverse Events Recording Guidelines for Phase II trials. Patients with an AE of > Grade 1 will be followed until the resolution of the AE to ≤Grade 1 or baseline. Serious AEs (SAEs) that occur within 30 days of EOT should also be followed and recorded.

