7.1 Safety Parameters

7.1.1 Definition of Adverse Event

The International Council on Harmonisation (ICH) Guideline for Good Clinical Practice (GCP) E6 defines an AE as “any untoward medical occurrence in a patient, or clinical investigation patient administered a pharmaceutical product and which does not necessarily have a causal relationship with this treatment”. An AE can, therefore, be any unfavorable and unintended sign (including an abnormal laboratory finding), symptom, or disease temporally associated with the use of a medicinal product, whether or not considered related to the medicinal product.

An AE includes but is not limited to any clinically significant worsening of a patient’s preexisting condition. An abnormal laboratory finding that requires an action or intervention by the investigator, or a finding judged by the investigator to represent a change beyond the range of normal physiologic fluctuation, should be reported as an AE.

AEs may be treatment-emergent (i.e., occurring after initial receipt of investigational product) or non-treatment-emergent. A non-treatment-emergent AE is any new sign or symptom, disease, or other untoward medical events that begin after the written informed consent has been obtained, but before the patient has received the investigational product.

Elective treatment or surgery or preplanned treatment or surgery (that was scheduled prior to the patient being enrolled in the study) for a documented preexisting condition, that did not worsen from baseline, is not considered an AE (serious or non-serious). An untoward medical

Proprietary Information of MD Anderson

Protocol 2020-1241

19 October 2022

event occurring during the prescheduled elective procedure or routinely scheduled treatment should be recorded as an AE or SAE.

The term AE is used to include both SAEs and non-serious AEs.

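### If the Phase II recording table is followed, non-serious Grade 1-2 AEs judged unrelated or unlikely stay out of the database, so the all-cause AE incidence in 3.2 and 8.1 can only be understated

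*Combined protocol and SAP*

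**What the plan says.** **Endpoint.** Section 3.2 lists as a safety endpoint the "Incidence of AEs including but not limited to treatment-emergent AEs, serious AEs, deaths, and clinical laboratory abnormalities", graded by CTCAE v5.0. It sets no limit by grade or causality. Section 7.1.1 separates the two kinds of event by timing only: "AEs may be treatment-emergent (i.e., occurring after initial receipt of investigational product) or non-treatment-emergent". The same section counts an event as an AE whether or not it is thought related.

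**Full collection.** Section 7.2 says "The investigator must report all AEs from the time of first protocol-specific intervention through 30 days following cessation of study treatment", and asks for a severity grade from 1 to 5 for each event. Footnote e of the Schedule of Assessments (Appendix A) has AEs captured from consent until 30 days after the last dose or the start of new anticancer therapy, with no limit by attribution.

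**Reduced collection.** Section 7.4.2 says "This study will follow the NCI Recommended AE Recording Guidelines for Phase II studies". Section 4.1.3 says the same: "AEs that occur prior to the safety follow-up visit will be recorded as per the NCI Adverse Events Recording Guidelines for Phase II trials". Reading across Grades 1, 2 and 3, the first rows of Table 17 are "Unrelated Phase I Phase I Phase I Phase II" and "Unlikely Phase I Phase I Phase I Phase II". Phase II first appears in both rows at Grade 3.

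**Analysis.** Section 8.1 plans AE summaries without a causality limit, then frequency, severity and duration for treatment-related AEs, and a Bayesian beta-binomial model for AE rates. Section 7.4.2 has AEs and SAEs recorded in MOCLIP, and 8.3.1 makes MOCLIP/CORe (or other databases) the eCRF.

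**The concern.** Staff cannot follow both collection rules. Under 7.2 and footnote e, a mild unrelated headache goes into the data. Under Table 17 it does not. Because the recording platform is also the eCRF, an event left out under Table 17 is absent from the data set on which the 8.1 summaries and AE-rate estimates are run.

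A table headed as treatment-emergent AEs, or simply as AEs, would then contain only related AEs, Grade 3 or higher AEs and SAEs. The trial is open-label and gives every patient the same combination. The investigator's causality call would therefore decide whether a non-serious low-grade event enters the database, and no control arm would show the effect. An event that was never entered cannot be re-attributed at analysis.

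**Working it through.** The plan gives no figure to reproduce, so the check compares the sections and then works out the direction of the effect.

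**Step 1: what the endpoint covers.** Section 3.2 has no causality or grade limit, and 7.1.1 defines treatment-emergent by timing. Together they describe all-cause, any-grade incidence. Section 3.2 does not say this in so many words; it follows from reading the two sections together.

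**Step 2: what Table 17 leaves out.** There are five attribution levels and two low grades, so 5 × 2 = 10 cells for Grades 1-2. Phase II is missing from 2 rows (Unrelated, Unlikely) × 2 grades = 4 of them. This counts table cells and says nothing about how many events fall in them. The two rows are complete in the text. The Possible, Probable and Definitive rows are partly merged, but every cell shown there includes Phase II.

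**Step 3: what is captured anyway.**

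| Component | Captured in full? | Where |
|---|---|---|
| SAEs, any grade or attribution | Yes | 7.6; recorded in MOCLIP per 7.4.2 |
| Deaths in the reporting period | Yes | 7.4.2.2 |
| Grade 3 or higher AEs | Yes | Table 17 |
| Possibly, probably or definitely related AEs | Yes | Table 17 |
| DLTs | Yes, limited to related events | 3.2 |
| Laboratory values with CTCAE grade | Yes, listed for every patient | 8.1.1 |
| Non-serious Grade 1-2 AEs judged unrelated or unlikely | No | Table 17 |

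Only the last row is lost.

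**Step 4: direction of the effect.** Recorded events are a subset of those that occurred. For a given AE term let f be the share of affected patients whose only occurrence falls in the last row of the table. Then

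recorded incidence = true incidence × (1 − f).

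Since f lies between 0 and 1, the recorded value can equal the true one or fall below it, but cannot exceed it. For the count of patients with at least one AE, a patient is lost only if every AE she or he had falls in that row.

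The beta-binomial estimate moves the same way. With a Beta(a, b) prior and x affected patients among n, the posterior mean is (a + x)/(a + b + n). The safety population fixes n, so a smaller x lowers the estimate, and the credible interval makes no allowance for events that were not entered.

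**Step 5: size.** The documents give neither the true incidence nor f. As an illustration only, assume a true any-grade incidence of 40%:

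- f = 0: 40% × 1.00 = 40%, no bias
- f = 10%: 40% × 0.90 = 36%
- f = 30%: 40% × 0.70 = 28%
- f = 50%: 40% × 0.50 = 20%

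**The case against.** **Nothing is lost if 7.2 is followed.** This is right, and the conclusion is therefore conditional. But 4.1.3 and 7.4.2 both state the reduced rule, and nothing visible gives 7.2 precedence. A distinction between reporting and recording does not settle it: 7.2 asks for event-level detail at Grades 1 to 5, and the recording platform is the eCRF.

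**Section 8.1 concentrates on treatment-related AEs, and no table of treatment-emergent AEs is named.** This is partly right. Frequency, severity and duration are promised for related AEs, which Table 17 supports in full. But 8.1 also promises AE summaries and AE-rate inference without that limit, and 3.2 names treatment-emergent AEs.

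**A reader might infer that the 3.2 endpoint cannot be computed, or that the four cells are never recorded.** Neither follows. Most components of the endpoint are complete, and a serious Grade 1-2 event is captured whatever its attribution. Section 7.3 also requires source documentation and an attribution for every AE, so the gap is in the database rather than in the patient record.

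**A reader might infer that dose confirmation in Part 1 is compromised.** The documents do not support that. Advancement depends on no more than 1 DLT (Section 5), and DLTs must be possibly, probably or definitely related, so none can fall in the omitted cells. The broader safety and tolerability objective of Part 1 is affected only descriptively.

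**Reduced Phase II recording is a legitimate choice.** It is. The fault lies in pairing it with an all-AE reporting rule and an unrestricted endpoint.

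**Withheld text might reconcile the rules.** The body of 7.7 and most of Section 8 before 8.1 are not visible, so this cannot be excluded.

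**Conclusion.** The inconsistency is real as the visible text stands. If Table 17 governs, the all-cause, any-grade AE incidence in 3.2, and the unrestricted AE summaries and AE-rate inference in 8.1, are incomplete and can only be biased downward. The loss is confined to non-serious Grade 1-2 events judged unrelated or unlikely, other than laboratory findings, which 8.1.1 lists anyway. The amount depends on how often low-grade events receive those attributions, which the documents do not state.

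The conclusion rests on two assumptions: that staff follow Table 17 over 7.2 and footnote e, and that no withheld section sets a different collection rule. The ORR analysis and the DLT rule are untouched. The point merits correction because the remedy is nearly free and stops a partial count from being presented as all-cause incidence.

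**What to change.** Reconcile 3.2, 4.1.3, 7.2, 7.4.2 with Table 17, 8.1 and Appendix A footnote e so that one collection rule applies. There are two ways:

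1. **Restate the endpoint (cheapest).** Keep Table 17. Word the 3.2 endpoint (and its copy in the synopsis) and the 8.1 summaries as treatment-related AEs of any grade, all Grade 3 or higher AEs, and all SAEs. Bring 7.2 and footnote e into line, and title the tables to match. The cost is wording only.
2. **Record everything.** Keep the all-cause endpoint and drop the Phase II restriction, so that every AE is entered whatever its attribution. The cost is modest extra data entry. Confining this to Part 1 is optional, since the DLT rule does not depend on it, and would leave Part 2 needing the wording in option 1.

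In either case, align the yes/no causality item in 7.2 with the five attribution levels in 7.3 and Table 17. A yes/no answer does not identify the table row for an event.

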7.4.2.1 Diagnosis Versus Signs and Symptoms

If known at the time of reporting, a diagnosis should be reported rather than individual signs and symptoms. However, if a constellation of signs and/or symptoms cannot be medically characterized as a single diagnosis or syndrome at the time of reporting, it is acceptable to report the information that is currently available. If a diagnosis is subsequently established, it should be reported as follow-up information.

Proprietary Information of MD Anderson

Protocol 2020-1241

19 October 2022

7.4.2.2 Deaths

All deaths that occur during the protocol-specified AE reporting period, regardless of attribution, will be reported to the appropriate parties. When recording a death, the event or condition that caused or contributed to the fatal outcome should be reported as the single medical concept. If the cause of death is unknown and cannot be ascertained at the time of reporting, report “Death of unknown cause”.

7.4.2.3 Preexisting Medical Conditions

A preexisting medical condition is one that is present at the start of the study. Such conditions should be reported as medical and surgical history. A preexisting medical condition should be reassessed throughout the study and reported as an AE or SAE only if the frequency, severity, or character of the condition worsens during the study. When reporting such events, it is essential to convey the concept that the preexisting condition has changed by including applicable descriptors (e.g., “more frequent headaches”).

7.4.2.4 Hospitalizations for Medical or Surgical Procedures

Any AE that results in hospitalization or prolonged hospitalization should be documented and reported as an SAE. If a patient is hospitalized to undergo a medical or surgical procedure as a result of an AE, the event responsible for the procedure, not the procedure itself, should be reported as the SAE.

Hospitalizations for the following reasons do not require reporting:

- Hospitalization or prolonged hospitalization for diagnostic or elective surgical procedures for preexisting conditions that were planned prior to the start of the safety reporting period
- Hospitalization or prolonged hospitalization required to allow efficacy measurement for the study
- Hospitalization or prolonged hospitalization for scheduled therapy of the target disease of the study

7.5 Assessment of Severity of Adverse Events

The severity of the AEs will be graded according to the **NCI CTCAE V.5.0**. Events not included in the NCI CTCAE will be scored as follows:

General grading:

- **Grade 1:** Mild: discomfort present with no disruption of daily activity, no treatment required beyond prophylaxis.
- **Grade 2:** Moderate: discomfort present with some disruption of daily activity, require treatment.
- **Grade 3:** Severe: discomfort that interrupts normal daily activity, not responding to first-line treatment.

Proprietary Information of MD Anderson

Protocol 2020-1241

19 October 2022

- **Grade 4:** Life-threatening: discomfort that represents an immediate risk of death

7.6 Serious Adverse Event Reporting Requirements for MDACC Sponsor Single Site Investigational New Drug (IND) Protocols

An adverse event or suspected adverse reaction is considered “serious” if, in the view of either the investigator or the sponsor, it results in any of the following outcomes:

- Death
- A life-threatening adverse event
- Inpatient hospitalization or prolongation of existing hospitalization
- A persistent or significant incapacity or substantial disruption of the ability to conduct normal life functions
- A congenital anomaly/birth defect
- Important medical events that may not result in death, be life-threatening, or require hospitalization may be considered a serious adverse drug experience when based upon appropriate medical judgment, they may jeopardize the patient or subject and may require medical or surgical intervention to prevent one of the outcomes listed in this definition. Examples of such medical events include allergic bronchospasm requiring intensive treatment in an emergency room or at home, blood dyscrasias or convulsions that do not result in inpatient hospitalization, or the development of drug dependency or drug abuse (21 CFR 312.32).
- Important medical events, as defined above, may also be considered serious adverse events. Any important medical event can and should be reported as an SAE if deemed appropriate by the PI or the IND sponsor, MDACC IND office.
- All events occurring during the conduct of a protocol and meeting the definition of an SAE must be reported to the IRB following the timeframes and procedures outlined in “The University of Texas M. D. Anderson Cancer Center Institutional Review Board Policy on Reporting Adverse Events for Drugs and Devices”.
- SAEs will be captured from the time of the first protocol-specific intervention, until 30 days after the last dose of the drug or protocol-specific timeline, unless the participant withdraws consent.
- SAEs must be followed until clinical recovery is complete, and laboratory tests have returned to baseline, the progression of the event has stabilized, or there has been acceptable resolution of the event.
- All SAEs, expected or unexpected/ initial or follow up, must be reported to the IND office within 5 working days of knowledge of the event regardless of the attribution.
- Death or life-threatening events that are unexpected, possibly, probably, or definitely related to the study treatment must be reported (initial or follow up) to the IND office within 24 hours of knowledge of the event.
- Additionally, any SAEs that occur after the 30-day time period or protocol-specific timeline that is related to the study treatment must be reported to the IND office. This may include the development of a secondary malignancy.

Proprietary Information of MD Anderson

Protocol 2020-1241

19 October 2022

- The electronic SAE application (eSAE) will be utilized for safety reporting to the IND office and MDACC IRB.
- All events reported to the supporting company must also be reported to the IND office.

Reporting to the FDA:

- Serious Adverse Events will be forwarded to the FDA by the IND sponsor (MDACC IND office) according to 21 CFR 312.32.

It is the responsibility of the PI and the research team to ensure serious AEs are reported according to the CFR, GCP, protocol guidelines, sponsor's guidelines, and IRB policy.

